To estimate the treatment effect for *longitudinally measured continuous outcomes*, the outcome will usually be defined as “change from baseline” (difference at follow-up visit minus baseline value). The treatment effect through follow-up will then be estimated with 95% confidence intervals using generalized estimating equations (GEE) with an indicator for treatment group, or, in the case of Gaussian responses, the corresponding mixed effects models with random effects for participants. To improve the model fit and reduce error variance, “visit number” (day) may be included as categorical variable in the model; alternatively, “time” may be included as continuous variable. Models will also be adjusted for the baseline values of the outcome variable.

Time-to-event outcomes will be summarized with Kaplan-Meier estimates for cumulative probabilities over time, and compared between treatment groups using stratified log-rank tests or Cox proportional hazards models, or their competing risk analogues.

In case “death” is a competing risk for the outcome (e.g., for time to hospital discharge), the following competing risk methods will be used:

- Aalen-Johannsen estimator for the cumulative incidence function (analogue to the Kaplan-Meier estimate)³
- Gray’s test with $\rho=0$ (analogue to the log-rank test)⁴
- Fine-Gray estimates and tests for the sub-distribution hazard ratio (analogue to the Cox proportional hazards model).^{5,6}

The proportional hazards assumption will be tested by adding an interaction term for time by treatment group to the model. The cumulative proportions of participants who experienced the event will also be compared at given time points (specified in secondary objectives, e.g., at 28 days); in this case, the cumulative proportions will be estimated using Kaplan-Meier estimates or the competing risks analogue, and/or as proportion of participants who reached the time point (e.g., time since randomization ≥ 28 days).

The **administrative follow-up time** is defined as the minimum of (cut date minus randomization date) or the analysis time period. For example, the analysis time period for the time to hospital discharge is 180 days, and the analysis time period for the important safety endpoint, the composite of *grade 3 and 4 events, SAEs, PSESEs, or death*, is 5 days or 28 days. The **administrative censoring date** is the earlier of the cut-date of the dataset or the randomization date plus analysis time period.

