Comment: The notion of “administrative censoring” is important in time-to-event analyses in the presence of competing risks. For example, the Fine-Gray method for estimating the sub-hazard ratio for time to hospital discharge can be approximated by using a Cox proportional hazards model where follow-up time for participants who died without being discharged is not censored at death, but is carried forward to the administrative censoring date with event status “not recovered”.

Censoring for time-to-event analyses

For **interim** analyses, the type of censoring used will depend on the data collection schedule.

- If the reporting of the endpoint is data-driven (e.g., SAEs and deaths are reported as they occur), then follow-up is censored at the administrative censoring date, at the date of withdrawal, or loss to follow-up, whichever occurs earliest.
- If the date of the event is elicited retrospectively at fixed study visits spaced more than one week apart, follow-up will be censored at the last day the endpoint status was ascertained. For example, this applies to endpoints that require information on whether the patient has been “at home” for a given period of time, such as time to *sustained recovery*.
- Sensitivity analyses will be provided for key analyses when the outcome status is uncertain.

For **final** analyses, follow-up will be censored on the last day the outcome status was ascertained.

Adverse events (AEs) will be classified by system organ class according to MedDRA®¹ (currently version 24.0 [March 2021] is used; when new versions are implemented, items are recoded). AEs will be graded according to the *DAIDS Table for Grading the Severity of Adult and Pediatric Adverse Events, Corrected Version 2.1 (July 2017)* (also referred to as the *DAIDS AE Grading Table*).⁷ Hypotension AEs will be graded according to Table D-3 in **Appendix D**; this table is replicated from the TESICO protocol, version 2.0, Table 5. Cause of death will also be coded according to MedDRA®.

Comment: Under version 1 of the TESICO protocol, hypotension AEs were graded according to the DAIDS AE Grading Table.

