 - Grade 3 and 4 AEs that occur peri-infusion (i.e., during and within 2 hours after the infusion) on Days 0-2 and are reported on the infusion eCRFs will be included as incident grade 3 or 4 AEs, unless noted otherwise.
 - The number and percent of participants with incident grade 3 and 4 AEs will be summarized by MedDRA® system organ class and grade, and by MedDRA® system organ class and grade cut-off (i.e., grade ≥ 3 , grade 4). Comparisons between treatment groups will be for the proportion of participants who experienced AEs of grade 3 or higher through Day 28, using stratified CMH tests or logistic regression, stratified by disease severity at study entry (*invasive mechanical ventilation or ECMO* vs. neither). Treatment groups will be compared for incidence of grade 3 or 4 AEs overall, and by system organ class.
 - System organ classes may be split up into MedDRA® preferred terms (PT) for the most frequent system organ classes, particularly for classes where the treatment difference is significant.
 - Other clinically meaningful AE groupings (beyond system organ class) may be developed by the study team, who are blinded to the treatment effect.
- Grade 1-4 clinical AEs are reported at baseline (Day 0 prior to infusion of the investigational agent), on Days 0-2 peri-infusion (during and within 2 hours after the

infusion), as well as on Days 14 and 28. The peri-infusion AEs are collected as “signs and symptoms” via checklist on the infusion eCRFs.

The analysis of peri-infusion AEs is described in section 6. In particular, the number and percent of participants with peri-infusion AEs will be summarized by day and grade, by type and grade, and by type and action taken (i.e., modification or discontinuation of the infusion).

- Treatment groups will be compared for the proportion of participants who developed **PSESEs** through Day 28 and through Day 90, using stratified CMH tests. In addition to the overall comparison, individual components of the composite PSESE outcome will be tabulated, and compared between treatment groups using stratified CMH tests. The components of the PSESE outcome are listed in [Appendix C](#).

Comment: The composite outcome of *clinical organ failure, serious infections, or death* is identical to the composite of all PSESEs; individual components of clinical organ failure are listed in [Appendix B](#).

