Treatment groups will also be compared for the incidence of PSESEs using time-to-event methods; because death is a PSESE, the overall comparison will use Cox proportional hazards models, while comparisons for individual components will use the Fine-Gray model to account for the competing risk of death. Models will be stratified by disease severity at study entry (*invasive mechanical ventilation or ECMO* vs. neither) if event numbers permit.

- Treatment groups will be compared for incidence of a composite of cardiovascular and thromboembolic events, a subset of the organ failure outcome (items b1, e2, e3, and f2 in [Appendix B](#)). Time-to-event methods will be used that take into account the competing risk of death (as described in section 3, using Aalen-Johansen estimates for the cumulative incidence functions, and Gray's and Fine-Gray's methods to compare treatment groups and estimate the sub-hazard ratio).
- **Subgroup analyses:** The impact of study arm on the primary safety outcome (composite of grade 3 or 4 events, SAEs, PSESEs, or death through Day 5) and other important safety outcomes will be assessed for subgroups defined by baseline characteristics, including demographics, duration of symptoms at enrollment, baseline classification of “home”, clinical history and presentation (including disease severity at study entry), use of concomitant medications, and, if available, baseline levels of antibodies, antigen and viral RNA; tests for homogeneity of the treatment effect across subgroups will be carried out. Outcomes and methods for subgroup analyses are described in detail in section 8.5.
- Treatment groups will be compared for mean changes in laboratory test values from baseline to Day 3, and for incidence of grade 3 and 4 laboratory abnormalities at Day 3 (new abnormality or increase in grade). Laboratory tests include the basic metabolic panel (BMP), complete blood count (CBC) with differential, international normalizing ratio (INR), D-dimer, AST, ALT, and bilirubin. Statistical methods are described in section 3. Biomarkers will be log-transformed as needed.
 - For all participants, these biomarkers will be determined locally on Days 0, 1, and 2. Treatment groups will be compared for mean changes from baseline through

Day 2, overall using longitudinal models, and pointwise at Days 1 and 2 using ANCOVA models; models will be adjusted for baseline biomarker levels.

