- Outcomes assessed in other treatment trials of COVID-19 for hospitalized participants in order to facilitate meta analyses and facilitate generation of norms, including an ordinal scale measuring the degree of oxygen support through Day 14, time to discharge from the initial hospitalization, and binary outcomes defined by worsening based on the worst 3 categories of the primary ordinal recovery outcome at day 90. We will try to match the analyses in the other trials, to get results that can be compared. These analyses will not be performed for interim reports to the DSMB, unless requested.

- A composite of cardiovascular events (outcomes listed in items b1, e2 and e3 in [Appendix B](#)) and thromboembolic events (item f2) through Day 28 and Day 90. Time to event methods will be used that take into account the competing risk of death, e.g., Gray's test to compare treatment groups.

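### PSESE components and the cardiovascular/thromboembolic composite are compared on cumulative-incidence measures only; a cause-specific hazard ratio should be added beside them

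*SAP*

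**What the plan says.** SAP Section 7.1 compares the individual PSESEs in two ways. On proportions through Day 28 and Day 90, "individual components of the composite PSESE outcome will be tabulated, and compared between treatment groups using stratified CMH tests". On time to event, "comparisons for individual components will use the Fine-Gray model to account for the competing risk of death".

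The cardiovascular and thromboembolic composite (Appendix B items b1, e2, e3 and f2) is analysed in Section 7.1 "using Aalen-Johansen estimates for the cumulative incidence functions, and Gray's and Fine-Gray's methods to compare treatment groups and estimate the sub-hazard ratio". Section 8.4 lists the same composite through Days 28 and 90: "Time to event methods will be used that take into account the competing risk of death, e.g., Gray's test to compare treatment groups".

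The general rule is in Section 3. Where death competes with the outcome, "the following competing risk methods will be used", and the list that follows holds Aalen-Johansen, Gray's test and Fine-Gray. The Section 3 comment on administrative censoring, which uses hospital discharge as its example, explains that follow-up of a participant who died without the event is "not censored at death, but is carried forward to the administrative censoring date". The SAP names no cause-specific hazard ratio for these outcomes.

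Death is handled elsewhere. For PSESEs overall, "because death is a PSESE, the overall comparison will use Cox proportional hazards models" (Section 7.1). Mortality has its own log-rank and Cox comparison (Section 7.1) and its own harm boundary (Section 10.2).

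**The concern.** Keeping the dead in the risk set as non-events suits recovery and discharge, where death is a failure and should lower the measure. For a harm such as stroke, renal replacement or thromboembolism, the same convention counts someone who died first as free of the harm. The comparison then reflects two things at once: how the drug changes the rate of the component among those still alive, and how many participants die before they can have it.

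Component comparisons exist to show which organ is affected. If the drug raises mortality, part of a real organ signal is removed. If it lowers mortality, organs that it does not touch appear slightly harmed. The death-inclusive PSESE analysis shows that an arm is doing worse but not through which organ.

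**Working it through.** The documents state no event rates and no figure for this analysis, so there is nothing of the plan's own to reproduce. All rates below are assumptions.

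**Inputs.** Control death hazard 0.0112 per day to Day 28, then 0.0019. Component hazard 0.012 per day to Day 28, then 0.0015. The two are independent. Group size is 320 per arm (SAP Section 1.4). Implied control mortality is 1 − exp(−0.0112×28) = 27% at Day 28 and 1 − exp(−0.3136 − 0.0019×62) = 35% at Day 90.

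**Formula.** With component hazard c and death hazard d, cumulative incidence to time t in the first period is F = c/(c+d) × [1 − exp(−(c+d)t)]. The second period adds the same expression multiplied by the fraction still free of both events.

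**Day 28, mortality HR 1.5, component unaffected.**
- Control: 0.012/0.0232 × (1 − exp(−0.6496)) = 0.247.
- Active: 0.012/0.0288 × (1 − exp(−0.8064)) = 0.231.
- Odds ratio: (0.2306/0.7694)/(0.2471/0.7529) = 0.91.
- Fine-Gray subdistribution hazard ratio (sub-HR): a hand approximation is ln(0.7694)/ln(0.7529) = 0.92. Fitting the model with deaths carried forward, as the Section 3 comment describes, gives 0.93.

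**Day 90, same scenario.**
- Control: 0.2471 + exp(−0.6496) × 0.0015/0.0034 × (1 − exp(−0.2108)) = 0.291.
- Active: 0.2306 + exp(−0.8064) × 0.0015/0.00435 × (1 − exp(−0.2697)) = 0.267.
- Odds ratio 0.89; fitted sub-HR 0.91.

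**Fitted sub-HR in other scenarios.**

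| Mortality HR | True component HR | Day 28 | Day 90 |
|---|---|---|---|
| 1.2 | 1.00 | 0.97 | 0.96 |
| 1.35 | 1.00 | 0.95 | 0.94 |
| 1.5 | 1.00 | 0.93 | 0.91 |
| 0.67 | 1.00 | 1.05 | 1.07 |
| 1.5 | 1.30 | 1.20 | 1.17 |
| 2.0 | 1.30 | 1.11 | 1.07 |

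**Day 5, mortality HR 1.5.** Control 0.012/0.0232 × (1 − exp(−0.116)) = 0.0567; active 0.012/0.0288 × (1 − exp(−0.144)) = 0.0559. The ratio is 0.986, a shift of about 1%.

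**Other assumptions.** I varied net component risk by Day 90 (10% or 25%), control mortality (25% or 40%), and the hazard shape (constant or front-loaded). At mortality HR 1.5 the sub-HR is 0.89–0.95 with no component effect and 1.15–1.24 with a true HR of 1.30. At mortality HR 1.2 with no component effect it is 0.95–0.98.

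**Effect on detecting a true component HR of 1.30 by Day 90.**
- Mortality unchanged: 0.291 versus 0.358. The difference of 0.067 over a standard error of 0.0369 gives z = 1.82 and power of about 44%.
- Mortality HR 1.5: 0.291 versus 0.329. The difference of 0.038 over 0.0365 gives z = 1.05 and power of about 18%.
- Cause-specific test in that second case: about 320 × (0.291 + 0.329) = 198 events, so z ≈ ln(1.30) × √198/2 = 1.85 and power is about 45%.

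**The case against.** The strongest reply is that cumulative incidence answers a legitimate question, namely how many participants actually experience the event. Fine-Gray is therefore not an error, and making the cause-specific HR the harm measure would only swap one valid estimand for another. That stands, and it is why the fix adds a measure and replaces none.

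Second, the shift is small against noise. A 25% component in 640 participants gives about 160 events and a standard error of the log HR of about 2/√160 = 0.16. Shifts of ln 0.93 = −0.07 and ln 0.91 = −0.09 are 0.5 to 0.6 of that. This limits the consequence for any one component, but a systematic shift in a known direction across components is still worth showing.

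Third, large distortions come with a visible mortality signal. At mortality HR 1.5 about 320 × (0.350 + 0.476) = 264 deaths are expected, so |Z| ≈ ln(1.5) × √(264/4) = 3.3, beyond the 2.0 SD harm boundary in Section 10.2. Cause of death is also summarised by arm, PSESEs and deaths are listed for the DSMB, and Section 7 counts a death in the organ failure/serious infection composite when its cause matches a component. These soften the gap but do not close it. They show that deaths are in excess, or describe the fatal cases, but give no between-arm estimate for the component net of other deaths. At mortality HR 1.35 the same calculation gives 253 deaths and |Z| ≈ 2.4 at the end, but only about 1.7 with half of those deaths.

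Fourth, the cause-specific HR recovers the input value above only because the two hazards were made independent. With a shared gamma frailty of variance 1 (also an assumption) and mortality HR 1.5, it is about 0.95 and 1.2 at Day 90 for component HRs of 1.0 and 1.3, against about 0.89 and 1.1 for Fine-Gray. It is closer, but also attenuated.

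**Conclusion.** The point stands as an inexpensive improvement to the safety analysis. In this SAP the PSESE components and the cardiovascular/thromboembolic composite are compared through Days 28 and 90 on cumulative-incidence measures alone. Under the assumed rates, the mixing with mortality is about 3% to 7% at mortality HRs of 1.2 to 1.35 and 7% to 9% at 1.5. It is negligible at Day 5.

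Three stronger readings might be inferred and are not supported.
- **That an arm with excess deaths would look safer on every organ.** This needs a component whose own hazard is barely changed. A true 30% increase is diluted but stays above 1 in every scenario examined, with mortality HRs up to 2.0.
- **That all organ-harm comparisons are affected.** Section 7.1 compares laboratory values by ANCOVA and longitudinal models. The Section 7.2 comparison of hypotension with organ dysfunction is at Day 5, where the effect is negligible.
- **That Fine-Gray or CMH is wrong here.** Both describe absolute risk properly; the gap is that nothing stands beside them.

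The size rests on event rates that the documents do not give and on independent hazards. The protocol text was not available, so the statement about what is planned concerns the SAP only.

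**What to change.** In Section 7.1, for each PSESE component and for the cardiovascular/thromboembolic composite, and in Section 8.4 for the same composite:

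- Add a cause-specific Cox HR with 95% CI, censoring at death, stratified by disease severity where event numbers permit, beside the planned Fine-Gray ratio.
- Show by arm, side by side, the Aalen-Johansen cumulative incidences of the component and of death without it.
- Keep the Fine-Gray and CMH comparisons as planned, and keep Fine-Gray as the main method for recovery and discharge.
- Add to Section 3 a sentence saying what each measure is for: cause-specific for the rate of the component among those alive, cumulative incidence for absolute risk.

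The cost is one more model per component on data already collected, and one extra column per safety table. The table note should say that the cause-specific HR is not an absolute risk and that it too is somewhat attenuated if death and the component share unmeasured risk factors.

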The primary safety outcome of *grade 3 or 4 AEs, SAEs, PSESEs, or death through Day 5* includes potentially infusion-related outcomes; the analysis of the primary safety outcome is described in section 7. The current section describes safety analyses that are focused on the peri-infusion time period (i.e., during and within 2 hours after the infusion).

Peri-infusion signs and symptoms are reported as AEs (with grade and action taken) on eCRFs. Local labs are reported at baseline, Days 1 and 2 for all participants, and Days 3 and 5 if clinically available. Labs on Day 5 are reported for participants who are treated in the ICU.

Side effects of aviptadil observed in previous studies include:

- Hypotension with and without vasopressor
- Diarrhea
- Facial flushing
- Bradycardia
- Tachycardia

For the aviptadil versus placebo comparisons, incidence and management of hypotension in particular will be monitored in detail. Blood pressure is recorded prior to the start of the infusion and every 2 hours peri-infusion on each infusion day. Vasopressor use and dose are reported: prior to the start of the infusion, the highest dose peri-infusion, and the dose at 2 hours after the infusion.

The following data summaries will be provided overall for Days 0-2, and separately by day. Treatment groups will be compared using statistical methods described under “analysis principles” in section 3; comparisons will be stratified by disease severity at study entry (2 categories, by use of *invasive mechanical ventilation or ECMO*).

- Number and percentage of participants with infusion-related signs or symptoms (reported during the infusion or within 2 hours after the infusion), by type and grade, by type and grade cut-off (i.e., \geq grade 2, \geq grade 3, etc.), and by type and action taken.

Comments:

1. For aviptadil, **diarrhea is not included in the composite safety outcome** of incident grade 3 or 4 AEs, SAEs, PSESEs or death unless it is a SAE or leads to discontinuation of the infusion (for the day, or permanent discontinuation). Therefore, peri-infusion diarrhea AEs will be summarized in two ways: (1) as reported, and (2) restricted to diarrhea AEs that lead to discontinuation of the investigational agent.
2. Hypotension, diarrhea, facial flushing, bradycardia, and tachycardia are collected as part of the infusion-related signs and symptoms, and will be summarized by type and grade, and by type and action taken in response to the AE, as described above.

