¹ Screening must be performed within 24 hours of randomization.

² These laboratory evaluations will only be performed as study procedures if they are unavailable clinically on that study day

³ Duration of study drug administration may vary by investigational agent; the sample provided here is for 3 successive days. Where the duration of study drug administration

varies from this schedule, the duration will be specified in the relevant agent-specific Appendix.

⁴ The Day 14 visit will record values for Days 8–14.

⁵ These will be not be collected after hospital discharge.

⁶ These laboratory assessments will only include clinically available results

⁷ It is acceptable to perform the Day 3 draw on Day 4.

⁸ The Day-5 draw will occur only among patients who remain in the intensive care unit (ICU) or equivalent. It is acceptable to perform the Day 5 draw on Day 5 \pm 1, but the Day 3 and Day 5 draws can not both be performed on Day 4.

⁹ Includes telephone administration of the Euro-QOL-5D-5L instrument.

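### Section 7.1 of the SAP compares graded laboratory abnormalities between arms only at Day 3, and plans no graded comparison on Days 1 and 2, when the panels are protocol-required

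*SAP*

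**What the plan says.** The laboratory bullet in SAP section 7.1 plans two comparisons at Day 3: mean change from baseline, and "incidence of grade 3 and 4 laboratory abnormalities at Day 3", defined as a new abnormality or an increase in grade. The sub-bullet says "For all participants, these biomarkers will be determined locally on Days 0, 1, and 2" and adds mean-change comparisons through Day 2 (longitudinal models) and at Days 1 and 2 separately (baseline-adjusted ANCOVA). A further sub-bullet adds mean changes through Day 5 for participants in the ICU on that day. Neither sub-bullet mentions grades.

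On availability, section 6.1 says "Local labs are reported at baseline, Days 1 and 2 for all participants, and Days 3 and 5 if clinically available". The schedule in Appendix E agrees. On-study labs run through Day 2, with footnote 2: "These laboratory evaluations will only be performed as study procedures if they are unavailable clinically on that study day". Days 3 and 5 sit in a separate row for clinical labs, with footnote 6: "These laboratory assessments will only include clinically available results". Footnote 5 covers both rows: "These will be not be collected after hospital discharge". Footnote 7 gives the Day 3 window: "It is acceptable to perform the Day 3 draw on Day 4".

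Two other places matter. Section 3 computes percentages from non-missing values when data are incomplete. Section 2 puts the incidence of grade 3 or 4 laboratory abnormalities in the weekly aviptadil report to the DSMB, without naming a day.

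**The concern.** The one graded laboratory comparison in section 7.1 falls on a day when the panel is not a study procedure. The two post-baseline days when it is a study procedure have no graded comparison. Aviptadil is infused on Days 0 to 2, so Days 1 and 2 are infusion days for that agent, and section 7.2 itself says that safety data on aviptadil are limited.

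Two things are at stake. A short-lived grade 3 or 4 abnormality can fall outside the comparison although its data were collected. And the Day 3 denominator depends on events after randomisation: survival, discharge and clinical ordering.

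**Working it through.** **Step 1: what is compared on each day.** The SAP gives no rate, power or sample size for laboratory abnormalities, so there is no planned figure to reproduce. Sections 6.1 and 7.1 and Appendix E, set side by side, give:

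| Day | Source of the panel | Mean change in 7.1 | Graded comparison in 7.1 |
|---|---|---|---|
| 1 | Protocol-required while in hospital | Yes | None |
| 2 | Protocol-required while in hospital | Yes | None |
| 3 | Clinically available only, while in hospital | Yes | Yes |
| 5 | Clinically available only, ICU | Yes | None |

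**Step 2: who is counted.**
- Grade 3 on Day 1, back to baseline grade on a Day 3 panel: in the denominator as a non-event.
- Grade 4 on Day 2, no Day 3 panel (death, discharge or not ordered): in neither numerator nor denominator, under the section 3 rule on non-missing values.
- Grade 3 on Day 2, still present on a Day 3 panel: counted.

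**Step 3: possible loss of power (illustration).** Inputs from the SAP: 320 per group (section 1.4) and two-sided 0.05 (section 3). Assumed: the event rates, the Day 3 availability and the share of the excess that has resolved. Availability is here taken as unrelated to arm and result. With n per arm and p̄ the mean of the two rates:

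power = Φ{ [ |pT − pC| − 1.96·√(2p̄(1−p̄)/n) ] / √([pC(1−pC) + pT(1−pT)]/n) }

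For 10% versus 18% and n = 320: (0.08 − 1.96 × 0.02743) / 0.02725 = 0.963, so power is 83%. For Day 3, n is 320 times availability. If half of the excess has resolved, the contrast becomes 10% versus 14%.

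| Day 3 results available | n per arm | Power, none resolved | Power, half of excess resolved |
|---|---|---|---|
| 95% | 304 | 81% | 33% |
| 85% | 272 | 77% | 30% |
| 70% | 224 | 69% | 26% |
| 50% | 160 | 54% | 20% |

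Rates of 15% versus 24%, or 20% versus 30%, start at 82% and 83% and stay within two percentage points of this table. In these scenarios, resolution costs more power than moderate missingness does.

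**Step 4: when missing panels bias the comparison.** Let a be the probability of having a Day 3 result, by arm and by whether the value is abnormal. With no true effect, the observed odds ratio is

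(a_abnormal,T / a_normal,T) / (a_abnormal,C / a_normal,C).

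Take 95% availability for abnormal participants in both arms (assumed):
- Normal participants 80% in both arms: odds ratio 1.00. A true 10% appears as 0.095 / (0.095 + 0.72) = 11.7% in each arm.
- Normal participants 80% (control) versus 70% (active): 0.80 / 0.70 = 1.14.
- Normal participants 90% (control) versus 70% (active): 0.90 / 0.70 = 1.29.

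A difference by arm is necessary for bias. It is not sufficient: if it is proportionally the same for normal and abnormal participants, the odds ratio stays at 1.00.

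**The case against.** The strongest reply is that little would go unseen. Mean changes are tested at Days 1 and 2 on the protocol-required panels. The weekly aviptadil report lists graded laboratory incidence with no day restriction. Clinical consequences such as hepatic decompensation, renal replacement therapy, disseminated intravascular coagulation and major bleeding are exempt serious events and enter the Day 5 primary safety composite. The DSMB may also ask for more summaries.

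This stands against the inference that laboratory toxicity on infusion days is missed altogether; the documents do not support that. It does not close the gap. A few grade 4 values can disappear in a mean, particularly after log-transformation. The weekly report covers aviptadil only, names neither day nor test, and its content may be modified by the DSMB. Appendix D describes collection of grade 3 and 4 clinical adverse events, so an isolated laboratory value may not reach the composite.

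A second reply is that Day 3 is a sensible day. It is the first scheduled panel certain to fall after the day of the last aviptadil infusion, which has the highest protocol-specified rate, and the SAP does not say whether the Day 2 panel precedes or follows that infusion. Remdesivir runs for up to 10 days, so Day 3 is normally still a treatment day for that agent. This stands in full: the infusion-day argument applies to aviptadil only, and replacing Day 3 with Days 1 and 2 could lose signal.

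A third reply is that few Day 3 panels may be missing in patients this ill, with a window that extends to Day 4. That is plausible, but the documents give no fraction. The Day 3 research draw in section 11 is for central testing and storage, and Appendix E still limits the Day 3 safety panel to clinical results.

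**Conclusion.** The gap is real and narrow. Section 7.1 specifies a graded laboratory comparison at Day 3 only, on clinically available results, and none on Days 1 and 2. Abnormalities that have resolved by Day 3, or that have no Day 3 panel after them, are left out of that comparison. The primary efficacy analysis, the primary safety endpoint and the mortality boundaries are unaffected.

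The size is unknown. The fall from 83% to between 54% and 81%, or to between 20% and 33% with half of the excess resolved, rests wholly on assumed rates, availability and resolution.

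Two further inferences should be avoided. One is that the Day 3 comparison is biased: that needs availability to differ by arm, and the documents give no evidence either way. If it does not differ, the cost is precision and inflated rates in both arms. The other is that every participant has panels on Days 1 and 2: collection stops at discharge.

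**What to change.** Add to section 7.1, for each agent's mITT cohort, a between-arm comparison of any new or worsened grade 3 or 4 laboratory abnormality relative to baseline. Use the worst grade through Day 2 (protocol-required panels) and, cumulatively, through Day 3. Test with the CMH test stratified by disease severity, and keep the existing exclusion of participants on dialysis at entry for renal tests.

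Keep the Day 3 comparison, and report beside it the number and percentage with a Day 3 result by arm. State how death, discharge and missing panels are handled. One workable rule is to count a participant as an event if any available panel in the window qualifies, and to list those with no post-baseline panel by arm and reason. Also state the day window for the graded laboratory line in the weekly report.

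The cost is SAP wording and a small amount of extra analysis on data already collected. The SAP already foresees an update by the blinded statisticians before unblinding.
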